2. Background: Tics in TS are thought to arise from 1) dysregulation of excitation/inhibition in brain regions related to motor function, and 2) alterations in specific brain chemistry that potentiates overexcitability in the primary motor cortex (M1), via input from the SMA. This results in the activation of striatal neurons, and hyper-excitation of the M1, leading to the expression of tics. It is hypothesized that TS is also associated with a reduction in GABA transmission within the SMA and M1 [3]. One technique that has shown promise in normalizing brain function and reducing symptoms of TS in children and adults is rTMS. While initial experiences with varied approaches were not encouraging [4] [5] an effective approach is emerging [6] [7] [8]. Furthermore, it is not known what effects this technique has on the concentration of brain metabolites that mediate cortical hyperactivity and inhibitory neurotransmission. In this study, we aim to investigate whether low frequency rTMS can improve TS symptoms in a pediatric population, and what effects this technique has on the concentration of brain metabolites that mediate cortical hyperactivity.

3. Novelty (What will we learn that we don't already know?): The neurobiological study of the novel application of rTMS in pediatric TS allows us to map the trajectory of adaptive changes in the brains of children with TS, and to attempt to speed up these processes as they relate to decreasing cortical hyper-excitability, modulating GABAergic neurotransmission, increasing inhibitory metabolite levels within affected brain regions. Our multimodal approach allows us to gain critical insight into the structural, functional, and metabolic correlates of TS symptoms within the pediatric brain, an area that currently remains underexplored.

4. Methods

Sample: A pilot cohort of 11 males with TS (7-12 years, right handed, no comorbid ADHD) will be recruited through the Calgary Tourette Syndrome Clinic (Alberta Children's Hospital, Calgary, Alberta). Participants will continue prescribed medication regimes during the trial at the discretion of individual medical care professionals.

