Measurements: To establish diagnosis and ascertain treatment response, we will conduct assessments at baseline, weekly during treatment (including the final week) and at 8 week and 6 month follow-ups. Measures used include the Yale Global Tic severity Scale (YGTSS), Present and Lifetime version of the Kiddie Schedule for Affective Disorders and Schizophrenia (K-SADS-PL), Multidimensional Anxiety Scale for Children, the Children's Depression Rating Scale-Revised, and the General Behavior Inventory (P-GBI).

MRI Acquisition: Participants will undergo both baseline and post-treatment MRI scans. MR data will be acquired on a GE 3T Discovery 750W scanner, and include a high-resolution anatomical scan for use in the rTMS procedure. Voxels within the M1 and SMA will be targeted by short echo (TE= 30msec, TR = 2000 msec) and MEGA PRESS proton magnetic resonance spectroscopy (1H-MRS) protocols. Analysis of MRS will be completed using the LCModel method, which converts the in vivo spectrum to a linear combination model for each metabolic solution [9, 10]. The SMA will be confirmed during the scan with a brief right and left finger tapping functional magnetic resonance imaging (fMRI) task [11]. We will also collect resting state fMRI and diffusion tensor imaging (DTI). Total time in the scanner is less than 60 minutes. Our established acquisition is well tolerated from ages 5 through adulthood.

Single and Paired-Pulse TMS (Neurophysiology): Using established lab protocols, the following motor neurophysiology measures (and their possible neurotransmitter system correlates) will be defined for M1 bilaterally at baseline and 1 week post-intervention: rest and active motor thresholds (RMT, AMT), stimulus response curve (100-150%RMT), short-interval intracortical inhibition (SICI, GABA_A), cortical silent period (cSP, GABA_B), ipsilateral silent period (iSP, interhemispheric inhibition), and intracortical facilitation (ICF, glutamatergic NMDA)[12].

Low-Frequency rTMS (Neuromodulation): Baseline T1 MR images will allow individualized neuronavigation (Brainsight 2, Rogue Research, Montreal QC) to coregister the rTMS Airfilm coil (Magstim, UK) precisely to the SMA as defined by fMRI. Interventional rTMS parameters will be: intensity 100% RMT, frequency 1Hz, duration 20 minutes (1200 stimulations). Treatments will occur on each weekday at the same time of day for three weeks (15 total).

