Analysis: Statistical analyses will be performed using SPSS for Windows 22.0 (SPSS Inc., Chicago, IL). For aim 1, to test for differences in tic symptoms (YGTSS) with rTMS, a repeated measures analysis of variance (rmANOVA) will be performed. A similar approach will be used for assessing glutamate concentration in the SMA, SICI, ICF, CSP (Aim 2). Furthermore for Aim 2, functional connectivity changes with rTMS will be examined using Statistical Parametric Mapping (SPM) approaches. Pearson correlations between clinical and neurobiological variables controlling for age will be explored.

5. Sample size with justification: Estimating the sample size needed was based on similar studies. For the primary outcome measure (aim 1) of a reduction in tic severity (Yale Global Total Tic Severity Scale), we set $p < 0.05$ (two tailed), $d = 0.47$, power = 0.80, rendering a need for a minimum of 10 subjects. Clinically meaningful change in the YGTSS will be defined at a 23% or greater reduction in total score [13].

6. Anticipated Results: We predict this novel treatment will demonstrate reduction in tic severity and intrusiveness. Potential pitfalls include (1) intolerance to rTMS, (2) inadequate MRI data quality and (3) non-response to treatment. For TMS tolerability, most do very well, with a low incidence of side effects [14]. Moreover, low frequency rTMS is the most well tolerated type of rTMS. With regard to motion during the MR scan, our group has scanned over 200 subjects at the Alberta Children's Hospital to date. Data loss from motion accounts for less than 5%. To improve data quality, we have a mock scanner that helps acclimatize children to the scanning procedure. Given our collaboration with the Calgary Tourette Syndrome clinic, we anticipate robust recruitment (over 1,000 patients associated with the clinic).

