7. Likelihood of Generating New Funding: In Canada, there are only 5 active operating CIHR grants with any conceptual relationship (however remote) with TS. Only two examine treatment (both behavioral interventions) and only one targets children, but simply as a sub-population. ClinicalTrials.gov has only two actively recruiting studies of TS listed in Canada as well (physical activity, pharmacological). **Despite the severity, prevalence, onset in childhood, and limitations of current interventions, there is little active research in TS in children.** Furthermore, despite the recent evidence described above implicating the SMA and indicating the promise of rTMS, no study is currently combining neurobiological measures with brain stimulation to target symptoms in TS. We believe, given our infrastructure and expertise, we are well suited to take leadership in this area internationally. Initial data will be applied to funding applications for the Thrasher foundation (\$300,000 over 3 years) and the Tourette Syndrome Association Research Grant (\$150,000 over 2 years). Similar funding will be sought from CIHR, AIHS, and NIH as appropriate. We have also formed a new collaboration with the Mayo Clinic, University of Cincinnati, CAMH, and others through our CAIRNS (Child and Adolescent International Research into Neuro-Stimulation) research program. This collaboration can help in developing larger scale trials.

Budget (How will the funds be spent? Include discussion of overlap with existing projects, if appropriate. Provide a justification and indicate the amount to be spent on each budget item).

Personnel

[Redacted personnel information]

Overlap

There is no overlap with existing projects. This direction into Tourette's Syndrome is entirely novel.

Please note that supplementary or "top-up" funding is not permitted for this competition; projects must explore a new avenue of research for the investigator.

Are there any other sources of funding? Yes: X - If yes, from where: [name] start up funds (\$4,950)

References:

1. Pringsheim T, et al; *Canadian journal of psychiatry Revue canadienne de psychiatrie* 2012, **57**(3):133-143.
2. Draper A, et al; *Current biology : CB* 2014, **24**(19):2343-2347.
3. Franzkowiak S et al; *PloS one* 2012, **7**(1):e27850.
4. Wile DJ; *Current treatment options in neurology* 2013, **15**(4):385-395.
5. Wu SW et al; *Brain stimulation* 2014, **7**(2):212-218.

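### The minimum of 10 subjects does not follow from d = 0.47, two-tailed 0.05 and 80% power alone, so the power claim is unsupported as printed

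*Combined protocol and SAP*

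**What the plan says.** Section 5 (Sample size with justification) gives the only reasoning for the sample size. It concerns the main endpoint ("For the primary outcome measure (aim 1) of a reduction in tic severity"), takes a two-tailed 0.05 level, and concludes "d = 0.47$, power = 0.80, rendering a need for a minimum of 10 subjects". The stated basis is one sentence: "Estimating the sample size needed was based on similar studies". Those studies are not named there. Section 2 (Background) cites earlier rTMS reports ("an effective approach is emerging [6] [7] [8"), but Section 5 does not link its effect size to them.

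The Analysis paragraph of Section 4 says that for Aim 1 "a repeated measures analysis of variance (rmANOVA) will be performed". It does not say which visits enter or which term is tested. The Measurements paragraph says "we will conduct assessments at baseline, weekly during treatment (including the final week) and at 8 week and 6 month follow-ups". With three weeks of treatment that is up to six visits: baseline, weeks 1 to 3, 8 weeks and 6 months. The Sample paragraph plans "A pilot cohort of 11 males with TS (7-12 years, right handed, no comorbid ADHD"), with no control group.

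**The concern.** For repeated measurements on the same children, d, the significance level and power do not fix a sample size. One also needs the SD by which d was standardised. If that is the spread between children, one needs the within-child correlation too, and for a repeated measures ANOVA the number of visits, the pattern of means and the tested term. None of these is printed. The most direct reading of a d for a within-child change gives a number nearly four times as large as 10.

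At stake is how an Aim 1 result will be read. If the design has much less than 80% power for 0.47, a non-significant result would look more informative than it is. Two things limit the consequence: the cohort is called a pilot, and the stated use of the results is modest ("Initial data will be applied to funding applications").

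**Working it through.** **Inputs from the documents:** two-sided alpha 0.05, d = 0.47, power 0.80, stated minimum 10 (Section 5); planned n = 11 (Section 4, Sample); up to six visits (Section 4, Measurements).

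**Assumptions, none in the documents:** the within-child correlation rho, the time courses, and compound symmetry (equal variances and equal correlations between visits). They are shown as ranges.

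**1. d in SDs of the pre-post change, two visits.** The test is a paired t, identical to a two-visit repeated measures ANOVA. The noncentrality is 0.47 × √n on n − 1 df.
- n = 10: 0.47 × √10 = 1.49, power 26.5%
- n = 11: 0.47 × √11 = 1.56, power 29.2%
- n = 37: power 79.4%; n = 38 is the first to pass 80%

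Turned round, the change detectable with 80% power is 0.996 SD of change at n = 10 and 0.938 at n = 11, about twice 0.47. The stated figure of 10 is not reproduced.

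**2. d in between-child SDs, two visits.** Here the effect in SDs of change is 0.47 / √(2(1 − rho)).

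| rho | Effect in SDs of change | n for 80% | Power at n = 11 |
|---|---|---|---|
| 0 | 0.332 | 74 | 17% |
| 0.3 | 0.397 | 52 | 22% |
| 0.5 | 0.470 | 38 | 29% |
| 0.7 | 0.607 | 24 | 44% |
| 0.8 | 0.743 | 17 | 60% |
| 0.9 | 1.051 | 10 | 88% |

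For n = 10 to give 80%, the effect must be 0.996, so rho = 1 − (0.47/0.996)²/2 = 0.889.

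**3. d in between-child SDs, six-visit overall test.** The noncentrality is n × Σ(mean at visit j − grand mean)² / (1 − rho), with 5 and 5(n − 1) df. The largest drop is 0.47 in each time course.

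| Assumed time course | n for 80% at rho 0.5 / 0.7 / 0.8 | rho needed for n = 10 |
|---|---|---|
| Immediate drop, held | 36 / 23 / 16 | 0.873 |
| Ramp over 3 weeks, held | 34 / 21 / 15 | 0.864 |
| Ramp, then half lost | 54 / 33 / 23 | 0.915 |
| Ramp, half lost at 8 weeks, all lost at 6 months | 40 / 24 / 17 | 0.883 |
| Most favourable: three visits at 0, three at full drop | 21 / 13 / 9 | 0.771 |

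**4. 0.47 read as Cohen's f.** The noncentrality is 0.47² × n × m / (1 − rho) for m visits.
- m = 2: 11 children at rho 0.5 (power 75.4% at n = 10, 80.2% at n = 11); 10 children at rho of about 0.555
- m = 4: 10 children at rho 0.3
- m = 6: 11 children at rho 0; 9 at rho 0.2

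This reading does reach 10 or 11. For two visits, however, f = 0.47 equals a difference of 2 × 0.47 = 0.94 between-child SDs, twice what the label d says.

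**The case against.** The strongest reply is that the original calculation may well have been valid. The plan is a repeated measures ANOVA with up to six visits, not a two-visit test, and several routes lead to 10 or 11. Cohen's f of 0.47 over six visits needs 11 children with no correlation at all. Taking f as d/2 = 0.235 over five visits at correlation 0.8 gives 10. A single contrast of baseline against the mean of five later visits, with a constant drop of 0.47 between-child SDs and correlation 0.8, has 82% power at n = 11. The unnamed similar studies may supply the missing inputs. The cohort is also a pilot, for which a small number is reasonable in itself.

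Much of this stands. A reader might infer that the trial needs 38 children. The documents do not support that: 38 belongs to one metric and a two-visit comparison that the plan does not name. A reader might also take 29% as the lowest possible power, which it is not, since smaller correlations give 22% or 17%.

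What does not stand is that the printed sentence suffices. Every route to 10 or 11 needs a visit count and an assumed correlation (even if zero) or a tested term that the plan does not state, and the Cohen's f route also contradicts the label. Nor does the pilot label settle it, because Section 5 justifies the number by 80% power for the primary outcome, not by feasibility or precision.

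**Conclusion.** The concern holds in a limited form: the 80% power claim for d = 0.47 with 10 subjects is unsupported as printed. It would go too far to call it false under every reading, because the documents do not show which metric, correlation, visits or test were used. On the ordinary paired reading of d, the planned 11 children have 29% power. With d in between-child SDs and two visits, power at 11 runs from 17% to 88% over correlations of 0 to 0.9. The six-visit overall test reaches 80% at n = 10 only for correlations of about 0.77 to 0.92. The six-visit figures also rest on the assumed time courses and compound symmetry. The point should be fixed because this sentence is the sole justification of the sample size for the primary outcome. It gives no reason to change the number of children.

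**What to change.** Keep 11 children and the repeated measures ANOVA. Amend Section 5 in this order.

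1. Recover the original calculation. If it gives 10, correct the effect-size label (to f, if that is what 0.47 is), and state the standardiser, within-child correlation, number of visits, tested term and source study.
2. If it cannot be recovered or does not give 10, remove the 80% power claim for d = 0.47 and state what the pilot delivers. Possible wording: *Eleven children is a pilot number. For a comparison of baseline with end of treatment it gives 80% power (two-sided 0.05) for a mean change of about 0.94 SD of the change scores, and about 29% power for a mean change of 0.47 SD.*

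That wording applies only if the sponsor chooses this contrast, which the plan does not name at present. If the overall visit effect is to be tested, the power figure should be given with its assumed correlation and time course.

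The cost is one or two sentences, with no extra patients and no change of analysis. The downside is that the stated power may become less favourable.
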